6. BASELINE AND FOLLOW-UP ASSESSMENTS AND LABORATORY EVALUATIONS

The following outlines the Data Paradigms for the CSC/PSC arm based on obtained values for various scales and data points utilized. The guidelines establishing blood pressure and cholesterol goals are from the American Heart and Stroke Association.⁸

A. On-Study/On-Intervention Evaluations

The schedule of evaluations occurring after randomization while the subject is on-study and on (or about to start) intervention along with allowable time window in which evaluations may take place (± 30 days with a target of ± 14 days) is shown in Table 7. Primary and secondary outcomes are considered a mandatory part of the protocol; remaining measures will be collected if patient/caregiver are able and/or available.

Table 7. Data Collection Paradigm: CSC/PSC Arm

Item/Metric	In Hospital Prior to Discharge	Post Discharge Visit												
		Day 0-14	Month of Visit to Home/Facility											
			1	2	3	4	5	6	7	8	9	10	11	12
Informed Consent Confirmed	X			X			X						X	
Demographics (Age, Gender, Race/Ethnicity, Marital Status, Zip Code of Residence, Income, and Education)*	X			X			X						X	
Caregiver/Family identified*	X			X			X						X	
Medical Record Number (MR #)*	X													
Get-With-The-Guidelines (GWTG) in-hospital data*	X													
Complications* ¹	X			X			X						X	
Patient Medical History	X			X			X						X	
National Institutes of Health Stroke Scale (NIHSS)*	X												X	
Stroke Subtype*	X													
Prior stroke/Transient Ischemic Attack (TIA)*	X													
Risk factor profile* ²	X												X	
Cholesterol panel or LDL*	X			X			X						X	
Hemoglobin A1C (HBA1C)*	X			X			X						X	
Perceived Support				SRU			SRU						SRU	

Stroke Impact Scale (SIS)				SRU			SRU						SRU
Simplified Modified Rankin Scale (smRS)	X			SRU			SRU						SRU
Blood Pressure (BP) Control: at target	X			X			X						X
Lipid Control: LDL, at target	X			X			X						X
Diabetes Control: HBA1C, at target	X			X			X						X
Smoking Status	X			X			X						X
Body Mass Index (BMI)	X			X			X						X
Diet Assessment	X			SRU			SRU						SRU
Exercise Assessment	X			SRU			SRU						SRU
Mortality surveillance				X			X						X
Recurrence surveillance				X			X						X
Readmission surveillance				X			X						X
Time at Home				X			X						X
Depression: Patient Health Questionnaire (PHQ-9)				X			X						X
Caregiver Strain Index (CSI)				X			X						X

RED=Primary and Secondary Outcomes, BLACK=Additional Assessments by Data Coordinator SRU=UAB's Survey Research Unit ¹Complications monitored: Urinary tract infection, pneumonia, aspiration, deep vein thrombosis, skin breakdown, fall, myocardial infarction, depression, fever/other infection, and Afib. ²Risk factor profile: hypertension, diabetes, hyperlipidemia, smoking status, BMI, Afib, family history. *Will be collected if patient/caregiver are able and/or available.
													

Intervention Discontinuation Evaluations. If the patient or caregiver/family declines follow up in-person visits, we will offer follow-up phone or virtual evaluations for primary and secondary outcomes and other assessments. If consent not provided for this, no follow up will occur.

Special Instructions and Definitions of Evaluations. Evaluations to be performed include: SIS and smRS, PHQ-9 depression scale, Caregiver Strain Index, blood pressure, Cholesterol panel, Hemoglobin A1c, BMI, Smoking cessation, exercise assessment, diet assessment, readmission, and recurrence, and others (see Table 7).

Final On-Study Evaluations. On study evaluations will be completed by the Coordinator and the University of Alabama Birmingham (UAB) SDCC Survey Research Unit (SRU) to include SIS and smRS, and other assessments (see Table 5).

Concomitant Interventions. None.

Study Intervention Modifications. None.

Assessments. Table 7 identifies and defines the assessments and the timeframe for each measurement parameter.

Other Laboratory Studies. None.

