6. BASELINE AND FOLLOW-UP ASSESSMENTS AND LABORATORY EVALUATIONS

The following outlines the Data Paradigms for Stroke Mobile based on obtained values for various scales and data points utilized. The guidelines establishing blood pressure and cholesterol goals are from the American Heart and Stroke Association.⁸

A. On-Study/On-Intervention Evaluations

The schedule of evaluations occurring after randomization while the subject is on-study and on (or about to start) intervention along with allowable time window in which evaluations may take place (± 30 days with a target of ± 14 days) is shown in Tables 7 and 8. Primary and secondary outcomes are considered a mandatory part of the protocol; remaining measures will be collected if patient/caregiver are able and/or available.

Table 7. Data Collection Paradigm: ISPU Arm, Stroke Central and Stroke Mobile

Item/Metric	In Hospital Prior to Discharge	Post Discharge Visit											
		Day 0-14	Month of Visit to Home/Facility										
		1	2	3	4	5	6	7	8	9	10	11	12
Informed Consent Confirmed	X	X	X	X	X	X	X	X	X	X	X	X	X
Demographics (Age, Gender, Race/Ethnicity, Marital Status, Zip Code of Residence, Income, and Education)*	X			X			X						X
Caregiver/Family identified*	X			X			X						X
Medical Record Number (MR #)*	X												
Get-With-The-Guidelines (GWTG) in-hospital data*	X												
Patient Medical History	X			X			X						X
Complications* ¹	X			X			X						X
National Institutes of Health Stroke Scale (NIHSS)*	X	X	X	X	X	X	X	X	X	X	X	X	X
Stroke Subtype*	X												
Prior stroke/Transient Ischemic Attack (TIA)*	X												
Risk factor profile* ²	X												X
Cholesterol panel or LDL*	X			X			X						X
Hemoglobin A1C (HBA1C)*	X			X			X						X
Perceived Support				SRU			SRU						SRU
Stroke Impact Scale (SIS)				SRU			SRU						SRU
Simplified Modified Rankin Scale (smRS)	X			SRU			SRU						SRU
Blood Pressure (BP) Control: at target	X	X	X	X	X	X	X	X	X	X	X	X	X
Lipid Control: LDL, at target	X			X			X						X
Diabetes Control: HBA1C, at target	X			X			X						X
Smoking Status	X	X	X	X	X	X	X	X	X	X	X	X	X
Body Mass Index (BMI)	X	X	X	X	X	X	X	X	X	X	X	X	X
Diet Assessment	X	X	X	X	X	X	X	X	X	X	X	X	X
Exercise Assessment	X	X	X	X	X	X	X	X	X	X	X	X	X
Mortality surveillance		X	X	X	X	X	X	X	X	X	X	X	X
Recurrence surveillance		X	X	X	X	X	X	X	X	X	X	X	X
Readmission surveillance		X	X	X	X	X	X	X	X	X	X	X	X
Time at Home		X		SRU			SRU						SRU
Depression History	X												
Depression: Patient Health Questionnaire (PHQ-9)		X	X	X	X	X	X	X	X	X	X	X	X

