- (1) The ISPU approach will improve secondary stroke outcomes relative to the CSC/PSC approach, including: SIS and smRS at 3 and 6 months, risk factor control, stroke recurrence rates, hospital readmission rates, mortality in the first 12 months, time at home, patient depression, and caregiver strain.
- (2) The ISPU benefit in SIS and smRS will persist after the protocol-based post-acute coordination of in-home/facility care is terminated (at 12 months).
- (3) Patient characteristics (specifically age, race, sex, income, and education) will affect the primary or secondary intervention differences.

B. Primary and Secondary Outcomes

Primary and secondary outcomes are documented in Table 1 and described below.

- *Primary outcomes* include patient function and QOL using the SIS and smRS at 12-months post-stroke.
- *Secondary outcomes* are patient/caregiver-centered and include: (1) short-term patient function and QOL using the SIS and smRS (at 3 and 6 months); (2) the proportion of patient with risk factors controlled at target (at 3, 6, and 12 months); (3) mortality in the first 12 months, time to first recurrent stroke, and number of hospital readmissions per participant month over the first 12 months; (4) Time At Home (proportion of survival time spent at home); (5) patient depression, using the Patient Health Questionnaire (PHQ-9; at 3, 6, and 12 months); and (6) caregiver strain, using the Caregiver Strain Index (CSI; at 3, 6, and 12 months).

Table 1. Study Outcome Measures and Assessment Frequency					
C3FIT OUTCOMES	VARIABLES	ASSESSMENT FREQUENCY (By Month)			
		H	3	6	12
Functional Assessment	Stroke Impact Scale	X	X+	X+	X+
Quality of Life	Simplified Modified Rankin Scale	X	X+	X+	X+
Stroke Risk Factors					
(8) Blood pressure control at target*	Standard Systolic and Diastolic Measurement	X	X	X	X
(9) Lipid control at target*	Standard Lipid Panel or, at a minimum, LDL (Blood Draw, repeated only if patient's cholesterol is elevated at baseline, if LDLC%≥70mg/dl, or if patient is on a statin)	X	X	X	X
(10) Diabetes control at target*	Standard HBA1c (Blood Draw, repeated only if patient's blood glucose is elevated at baseline or if HBA1C%≥7mg/dl)	X	X	X	X
(11) Smoking status*	Question(s) to assess patient smoking status	X	X	X	X
(12) Body Mass Index (BMI)*	Weight and hip circumference	X	X	X	X
(13) Diet	Question(s) to assess patient adherence to recommendations of the American Heart Association (AHA).	X	X+	X+	X+

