## **2. Definitions and classification of covariates**

The covariates used in the incremental models include measures of stroke severity, demographic factors, and traditional cerebrovascular risk factors.

- Measures of stroke severity
  - Discharge location, classified as discharged home vs. not home (skilled nursing, rehabilitation center, etc.).

- Discharge mRS, categorized as 0, 1, 2, 3 or 4 or more (noting relatively few patients with discharge mRS of 5).
- Discharge NIH Stroke Scale (NIHSS), categorized into approximate quartiles of 0, 1, 2-4 or 5+
- Stroke subtype (hemorrhage vs. infarction)
- Demographic factors
  - Age, considered as a continuous factor
  - Male sex
  - Race/Ethnicity, categorized as non-Hispanic white (NHW) versus not NHW (including both other races and Hispanic participants)
  - A summary neighborhood index of socio-economic status (nSES) based on previously published methods, including six variables representing wealth/income, education and occupation: (1) log of median household income, (2) log of median value of owner-occupied housing units, (3) proportion of households receiving interest, dividend, or net rental income, (4) proportion of adults aged  $\geq 25$  years with a high school diploma, (5) proportion of adults aged  $\geq 25$  years with college degree, and (6) proportion of people employed in executive, managerial or professional occupations.
- Baseline cerebrovascular risk factors
  - Cigarette smoking, categorized as current vs. non-current (past or never)
  - Hypertension as a dichotomous variable
  - Dyslipidemia as a dichotomous variable
  - Diabetes as a dichotomous variable
  - Atrial fibrillation or irregular heartbeat as a dichotomous variable
  - Sedentary activity (defined as a score of 0-No Physical Activity or 1-Sedentary or sitting most of the time)

Because the mixed models will include baseline assessment of the outcome variable (i.e., outcomes include measures at times 0, 3, 6, and 12 months), covariates directly related to the outcome being assessed will be excluded from the model. That is, variables will not be used as both an outcome and as a predictor in the same model. For example, discharge mRS will not be included in the models predicting treatment differences in mRS, and baseline hypertension will not be included in models assessing treatment differences in SBP. Rather, changes from baseline to the 3, 6 and 12-month visits will be assessed using contrast statements.

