#### **4.3. Depressive symptoms**

Depressive symptoms will be assessed using the PHQ-9 dichotomized at scores of 0 to 9 versus 10 and above (note that if fewer than 10% of patients present with depressive symptoms the score will be dichotomized at the median). The analysis of this outcome will then follow the approaches described above for dichotomous outcomes measured only at follow-up (i.e., adherence to exercise and diet guidelines).

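### The planned PHQ-9 comparison is not adjusted for pre-existing depression: the dedicated history item is scheduled in the ISPU arm only, neither arm has a pre-intervention PHQ-9, and the SAP lists no depression covariate

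*Protocol*

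**What the plan says.** The protocol is written as two arm-specific texts, each with its own Table 7 in section 6.A.

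- **ISPU Table 7** has an in-hospital row "Depression History", in addition to "Patient Medical History". PHQ-9 is blank in hospital and then marked at every visit from the first post-discharge visit to month 12.
- **CSC/PSC arm** ("Table 7. Data Collection Paradigm: CSC/PSC Arm"): there is no depression-history row. The row "Depression: Patient Health Questionnaire (PHQ-9" is marked at months 3, 6 and 12 only. "Patient Medical History" is collected in hospital here too, but its content is not itemised.
- **Both arms, Table 7 footnote 1**: the monitored complications include depression ("skin breakdown, fall, myocardial infarction, depression, fever/other infection, and Afib").
- **Protocol section 1.B**, both arms: the secondary outcome is "patient depression, using the Patient Health Questionnaire (PHQ-9; at 3, 6, and 12 months". Table 1 shows no hospital assessment.
- **SAP section 2**: "The covariates used in the incremental models include measures of stroke severity, demographic factors, and traditional cerebrovascular risk factors". The itemised list contains no history of depression and no mood measure.
- **SAP section 4.3**: PHQ-9 is split at 0 to 9 versus 10 or more and handled like "dichotomous outcomes measured only at follow-up".
- **SAP section 1**: 24 sites were randomized and 21 are analysed. The four incremental models are justified by the risk that randomizing sites leaves important factors unbalanced.

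**The concern.** With 21 sites, the proportion of patients with prior depression can differ between arms by several points through chance alone. Prior depression is an obvious candidate predictor of a PHQ-9 score of 10 or more. The SAP's reason for incremental adjustment applies directly, yet no adjustment level contains a depression term.

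Other outcomes have some anchor at baseline. mRS and SIS are analysed as change from month 0, and the six intermediate factors are restricted to patients not in control at discharge or baseline. PHQ-9 has neither a baseline value nor a substitute for one. The ISPU schedule also includes depression intervention where needed (Table 8), so readers will look for an effect here, and a chance difference that predates the stroke could resemble such an effect or mask it.

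The uneven schedule adds a practical hazard. The obvious variable to reach for later is a dedicated item in one arm with no scheduled counterpart in the other.

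**Working it through.** The documents give no power, event rate or depression prevalence for PHQ-9, so there is no plan figure to reproduce. The check has two parts.

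**1. Schedules side by side**

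| Item before month 3 | ISPU | CSC/PSC |
|---|---|---|
| Depression history, own row | In hospital | Absent |
| Medical history, not itemised | In hospital | In hospital |
| Complications (depression named) | In hospital | In hospital |
| PHQ-9 in hospital | No | No |
| PHQ-9 after discharge | From first visit | None |
| Depression covariate in SAP | None | None |

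The complications item records depression as a complication, so it does not stand in for prior history. The early ISPU scores come from Stroke Mobile visits, so they are not a clean baseline.

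**2. Illustrative size**

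*From the documents:* 21 sites; 1,262 patients (protocol Summary), so m = 1262/21 ≈ 60 per site.

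*Assumed:* 10 versus 11 sites; prevalence of prior depression p = 0.22; between-site SD s = 0.05 to 0.10; risk of PHQ-9 ≥ 10 with/without a history of 0.40/0.18 (difference 0.22) or 0.45/0.15 (difference 0.30).

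*Variance of the arm difference in prevalence:* V = [s² + (p(1−p) − s²)/m] × (1/10 + 1/11)
- s = 0.05: [0.0025 + 0.1691/60] × 0.1909 = 0.001015, SD 3.2 points
- s = 0.10: [0.0100 + 0.1616/60] × 0.1909 = 0.002423, SD 4.9 points

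*Shift in the crude PHQ-9 difference at 2 SD:* 2 × SD × risk difference
- Low: 2 × 0.0319 × 0.22 = 1.4 points
- High: 2 × 0.0492 × 0.30 = 2.95 points

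*Variance removed by adjustment:* H = (risk difference)² × V. *Variance that remains:* R = (w/m) × 0.1909, where w = p·r₁(1−r₁) + (1−p)·r₀(1−r₀) and r₁, r₀ are the risks with and without a history.
- Low: H = 0.0484 × 0.001015 = 0.0000491; w = 0.1679; R = 0.000534; H/(H+R) = 8%
- High: H = 0.09 × 0.002423 = 0.000218; w = 0.1539; R = 0.000490; H/(H+R) = 31%

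The standard error √(H+R) is 2.4 to 2.7 points.

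*With a residual ICC of 0.05* (the protocol's planning value for SIS in section 9.A; its use for PHQ-9 is an assumption): R = w × [0.05 + 0.95/60] × 0.1909
- Low: R = 0.00211, cut 2%
- High: R = 0.00193, cut 10%

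The standard error rises to about 4.6 points. Simulation of the same set-up gives slightly lower upper ends, 8 to 29% and about 2 to 9%.

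*Second set of assumptions:* p = 0.15 to 0.35, ICC of history 0.01 to 0.05, PHQ-9 ≥ 10 in 15% without a history and 2 to 3 times as often with one. SD = √{p(1−p)[1+(m−1)ICC](1/(10m)+1/(11m))}, which runs from 2.5 points (p = 0.15, ICC 0.01) to 5.3 points (p = 0.35, ICC 0.05). At 1.96 SD the imbalance is 5.0 to 10.5 points. The shift is 0.050 × 0.15 = 0.7 points at the low end and 0.105 × 0.30 = 3.1 points at the high end.

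Both sets give a shift of about 1 to 3 points.

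**The case against.** The strongest reply has four parts.

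- **Adjustment may already be possible.** A reader might infer from the missing row that the comparison cannot be adjusted. The documents do not show that. Both arms schedule a medical history in hospital, and nothing says it omits depression. The separate ISPU row hints that the general history may not capture it reliably, but does not prove it. This part of the reply stands: the gap lies in the plan and is not shown to be in the data.
- **Some of the imbalance is removed.** A reader might also infer that any imbalance survives every model. Models 2 to 4 adjust for severity, age, sex, race/ethnicity, neighbourhood SES and risk factors, and so remove whatever part of the imbalance is correlated with these. This stands; only the remainder is at issue.
- **The missing baseline PHQ-9 is not a CSC/PSC defect.** Neither arm has one, and follow-up-only analysis is stated for both. This stands.
- **The effect is small.** A 1-SD imbalance shifts the estimate by 0.7 to 1.5 points, against a standard error of at least 2.4 points. With site as a random effect, the SAP's first choice, chance imbalance is already reflected in that standard error. It is imprecision, not systematic bias. This stands for chance imbalance. Patients consent after their site is randomized, so differential enrolment is conceivable, but the documents contain no evidence of it.

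What remains is that no pre-stroke depression measure is named for an outcome whose SAP relies on covariates to handle imbalance.

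**Conclusion.** The point holds as a gap in the planned adjustment of one secondary outcome. The listed covariates may absorb part of an imbalance in prior depression; the rest stays in the estimate as imprecision. Its size is modest: about 1 to 3 percentage points on the crude difference at a 2-SD imbalance. The variance reduction from adjusting is roughly 8 to 30% if nothing else varies between sites, and roughly 2 to 10% if residual ICC is 0.05. The second range is the safer guide, since some other site variation is likely.

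Every depression input, and the 10 versus 11 split, is an assumption. The documents do not support the stronger conclusions that adjustment is impossible or that the comparison is systematically biased. The change is worth making because it is cheap and follows the SAP's own reasoning.

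**What to change.** 1. State whether the in-hospital medical-history field records depression in both arms.
2. If it does, pre-specify prior depression (yes/no) from that field as a covariate in the adjusted PHQ-9 models of SAP section 4.3.
3. If it does not, add the history item to the CSC/PSC Table 7. For patients already enrolled, abstract it from the chart with the same source and definition in both arms. Medical record numbers are scheduled for collection in both. Do not set the ISPU-only item against retrospective CSC/PSC charts: ascertainment would then differ by arm, and adjusting for it could itself introduce bias.
4. If common ascertainment is not possible, leave the covariate out and state the limitation.

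The cost under step 2 is one covariate. Under step 3 it is also one chart item per patient, up to 1,262 charts. The SAP describes data provision in the past tense, so most of that work may be retrospective.

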7. MANAGEMENT OF ADVERSE EXPERIENCES

Adverse experiences are anticipated to be rare. This study does not involve agents or interventions that are likely to be associated with adverse experiences. This study will use the standardized JC and ASA national guidelines for stroke care management. As revisions occur to the national guidelines these will be made available to clinical sites to modify their clinical site stroke patient care management strategies.

8. INTERVENTION DISCONTINUATION

A. Data and Safety Monitoring Board (DSMB)

A formal Data and Safety Monitoring Board (DSMB) will be convened at regular intervals (for example, twice a year) to review recruitment, data security, and patient safety. We do not anticipate adverse events from this intervention, but the DSMB will monitor overall outcomes, including the following: death, recurrent stroke, rehospitalization, serious hemorrhage, recurrent or new ischemic event, serious adverse experiences, and premature withdrawal from the study. This study does not involve agents that likely will be associated with adverse experiences; as such, the DSMB will have a follow-up schedule and Significant Adverse Effects (SAE) reporting schedule that will include regular meetings with possible emergency meetings.

Data and Safety Monitoring Plan. The DSMB is tasked with mandating specific data required for independent analysis. A formal DSMB Plan will be developed by the DSMB Chair and the CCC and SDCC PIs that includes a framework for monitoring of study data and process, clinical and primary/secondary outcomes and will be submitted to the full DSMB. The frequency of data and safety monitoring will be determined in consultation with PCORI.

B. Adjudication Committee (AC)

In addition to the PI, two vascular neurologists will be charged with adjudicating stroke-related hospitalizations reported during the follow up period. This group (the Adjudication Committee) will review specific outcomes, including recurrent stroke, including subtype; and serious hemorrhage, including site.

C. Criteria for Intervention Discontinuation

- Revocation of informed consent.
- Subjects moving substantial distance from the original geographical location.
- Morbidity or mortality giving rise to insurmountable barriers to continued assessment.

9. STATISTICAL CONSIDERATIONS

C3FIT will compare the effectiveness of the *JC-certified CSC/PSC care system with the ISPU care system* in improving patient outcome and quality of life post-stroke. The primary outcome is the SIS-3.0 at 12 months, while assessment at 3 and 6 months are part of secondary outcomes. The primary analysis will focus on intervention differences in mean SIS score at 12 months. Mixed models will be used to assess the SIS outcome at 12 months, allowing the hierarchical nature of the data to be reflected (patients within Sites), and providing an accounting for data that are not missing completely at random. We anticipate (and trust) that randomization will balance potential confounding factors; however, secondary analysis will be performed with adjustment for baseline factors that could be imbalanced and potentially confound the estimated intervention differences, specifically adjusting for factors assessed at baseline that are known to be strongly associated with stroke outcomes (specifically age and stroke severity). Patients who die or cannot return due to morbid conditions will be assigned to “floor” score for poor outcome (and hence does not reduce the number of evaluable patients). With these patients not representing missing data, we anticipate there will be relatively little additional missing data and that these data will be generally missing at random (i.e., patients

not returning because of other conditions, like moving); however, missing data that is present will be addressed by including baseline, 3 and 6 month data in the model and allowing the mixed model to adjust estimates for the missing data at 12 months by incorporating information available through the correlation between measurements.

A. Sample Size

The total sample size for the primary outcome for this study will be approximately 1,800 patients (each arm anticipated to have approximately 900 patients with approximately 100 patients, at each clinical site), although some sites will enroll up to 140 consented participants due to limited enrollment by other sites due to institutional COVID PANDEMIC issue. We have intentionally restricted clinical site participation to those Sites certified as a TJC CSC/PSC (or acting as such). This restriction is important not only to provide CSC/PSC intervention “state of the art” comparator group, but also to increase the homogeneity of Sites and, thereby, reduce intraclass correlation coefficient in the hierarchical models. We do not have information on the intraclass correlation coefficient of the SIS, but given this restriction, we would suggest it is quite small (0.01); however, for power calculations, we have conservatively assumed it is of modest size (0.05) and also provide estimates should it be large (0.10). These larger intraclass correlations would arise if there is larger than anticipated heterogeneity of intervention effect, and that there is adequate power for these larger intraclass correlation coefficients shows that we are well-positioned to detect intervention even in the presence substantial heterogeneity of the effect. Under this assumption and with the standard deviation of the SIS being approximately 8⁴⁹, if the interclass correlation is 0.05 then mean intervention differences of 2.7 and 3.2 can be detected with 80% and 90% power respectively (power calculations by PASS, NCSS, Kayville, UT); 2.7 was chosen based on evidence from Lin et al³⁰. Even if the intraclass correlation is 0.10, differences of 3.7 and 4.3 can be detected with 80% and 90% power. As such, we have quite good power to detect clinically significant differences generally smaller than half of a standard deviation of the outcome scale.

B. Analyses

Analysis of the primary analysis will focus on intervention differences in mean SIS and smRS scores at 12 months. In addition, the mixed models will be used to assess the SIS and smRS outcomes at 12 months, allowing the hierarchical nature of the data to be reflected (patients within Sites), and providing an accounting for data that are not missing completely at random. Analyses of the secondary outcomes of time either rehospitalization or subsequent stroke will be assessed using proportional hazards analysis. In order to incorporate the hierarchical nature of these data, this analysis will be implemented using packages such as the SURVIVAL procedure from the SUDAAN package (Research Triangle Institute, Research Triangle Park, NC).

Analysis of the QOL secondary outcome will follow the analysis approach as the primary analysis and will have similar power (i.e., ability to detect intervention differences of magnitude of a half-standard-deviation). The study will also focus on identifying specific subgroups who are particularly responsive or resilient to intervention differences.

